 - i. Will receive usual care, which may include pharmacist consultation and/or after-discharge phone call(s) if clinically necessary.
- g. Critical covariates, including, age, sex, gender, all recorded diagnoses, number of medications, all recorded medication types, zip code, first language, marital status, employment, social history (e.g. tobacco use, alcohol use) will be extracted from electronic health records (EHR) after the intervention ends at each study site. The complete list of data elements to be extracted from the EHR for evaluating trial outcomes are provided in **Appendix A**.

(2) Qualitative study to study barriers and facilitators of implementing PHARM-DC:

- a. In the first year of the intervention, the investigators ([name] and [name]) will visit trial sites to conduct 6 focus groups of 6 to 8 clinicians. These focus groups will be grouped by type of clinician (pharmacist, pharmacy tech, physician, nurse). We estimate that 48 people per site will participate in the study.
- b. We will use a purposive sampling design by role and department to determine eligibility.
- c. Eligible participants will receive an email from study staff inviting them to participate in the focus groups.
 - i. Documents:
 1. Recruitment email
 2. Information sheet
- d. Focus groups will be 60-90 minutes and will be administered by the PI, the qualitative researcher, and study staff. Due to COVID-19, the focus groups may take place virtually using video conferencing software (e.g. Webex).
- e. We may also conduct phone or video interviews in lieu of focus groups if individuals are not available for the focus groups.

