5.2 EXCLUSION CRITERIA

Exclusion criteria include the following:

- Expected discharge to another state, acute care facility, psychiatric facility, or locked facility (including locked skilled nursing facility, jail, or prison) **OR**
- Expected leaving hospital against medical advice (AMA) or actual AMA **OR**
- Homeless **OR**
- On hospice **OR**
- Already enrolled into study during prior discharge in previous year **OR**
- Expected to receive pharmacist-led post-discharge medication management regardless of the trial **OR**
- Patients admitted by admitting or attending Primary Medical Doctors who have a specialty that is not Internal Medicine or Family Medicine **OR**
- Expected post-discharge setting not conducive to the studied medication management intervention **OR**
- Patients admitted with a suspected or confirmed diagnosis of COVID-19.

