8.2 SAMPLE SIZE DETERMINATION

We will use a two-sided likelihood ratio test to compare the proportion of patients with utilization within 30 days of discharge between the intervention and usual care groups. Assuming 80% power and a type I error rate of 0.05, a two-sided Z test between two proportions with **4,888 subjects per group** would detect a difference of at least 2.49% from a baseline of 27.5%. Thus, our primary statistical analysis will be a two-sided Z test. We will also compare the baseline characteristics of those subjects across both arms to ensure there are no major differences. All enrolled patients will be analyzed.

Table 5 shows that varying the baseline utilization proportion does not substantially alter the minimum detectable difference. We also performed a sensitivity analysis assuming that 7.5% of patients in the intervention arm were unreachable or refused a phone call. Even at this rate, which is our best estimate from our pilot data, we would have 80% power to detect a difference of 2.54%. Finally, these rates were robust to contamination rates of 2% among patients in the usual care arm. We believe this low rate is a reasonable estimate for contamination, because patients thought to have a clear need for these services will be excluded from the RCT, and because we believe that non-pharmacist clinicians will remain so busy that they will not begin to provide such services to other patients.

Table 5. How Baseline Utilization Affects Minimum Detectable Difference

Percentage of Patients with Utilization within 30 Days of Hospital Discharge		
Usual Care	Intervention	Minimum detectable difference
30.0%	27.44%	2.56%
27.5%	25.01%	2.49%
25.0%	22.59%	2.41%

For the qualitative study, the study will enroll up to 48 people in the focus groups, 15 people in the Year 2 interviews, and 50 people in the interviews per site.

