To assure that the time-use data is representative, we will sample approximately 100 patient interactions (20 complete interventions, 20 discharge medication reconciliations, 20 post-discharge phone calls, and 40 observations of usual care) by study pharmacists at each study site over a one-year period. To ensure that pharmacists have become efficient in providing the intervention, sampling will only occur in years two and three and pharmacists with less than two-months experience with the intervention will be excluded.

Time spent on PHARM-DC activities for study subjects by the number of days since discharge. For example, we will identify all study subjects for which study pharmacists spent time on post-discharge day 1, etc. This will enable us to calculate the mean amount of pharmacist time necessary to provide the PHARM-DC intervention on each post-discharge day, and then the mean total time across all days. After estimating the mean total time per patient, we will apply National Bureau of Labor Statistics wage and benefit data to calculate the intervention's program cost per patient².

Next, we will calculate the mean program cost necessary to avert each measured utilization event (e.g., readmission) by multiplying the number needed to treat to prevent the utilization event by the cost of applying the intervention to one patient. For some hospital decision makers, we expect this data, in combination with hospital-specific costs, to be useful in deciding whether (and to what extent) to implement PHARM-DC. One example of hospital-specific costs would be anticipated HRRP costs (CMS readmissions penalties).

Costs of Post-Discharge Utilization: We will ascertain the total cost of all readmissions, observation stays, and ED visits with 30 days of discharge for all trial patients. At least 80% of patients are likely to return to the study hospitals; in this case, we will obtain charge data for the return visits and apply hospital-specific cost-to-charge ratios provided by hospital administrators. For return visits to outside hospitals, we will obtain charges for inpatient hospitalizations and ED visits using statewide data sets and calculate costs by applying cost-to-charge ratios for hospital services published by the Centers for Medicare and Medicaid Services.

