Net Costs: Next, we will calculate net cost for each patient from the health system perspective by subtracting the cost of any post-discharge utilization from any program costs (program costs are zero in the control group). Because we will apply a 30-day time horizon, discounting will not be used. We will calculate and test differences in mean values. Finally, we will calculate the difference between the intervention and control group to estimate incremental net costs per patient from the health system perspective.

8.4.5 SECONDARY DATA ANALYSIS: EXAMINE EFFECTS OF PHARM-DC INTERVENTION ON INITIATION AND DEPRESCRIBING OF BENZODIAZEPINE-RECEPTOR AGONISTS

The following secondary analyses of trial data are planned to examine effects of the PHARM-DC intervention on (1) the initiation of new outpatient prescriptions of benzodiazepine-receptor agonists (BZRs) and (2) the deprescribing of BZRs among patients taking BZRs prior to hospitalization:

1. Among patients without a BZR prescription on admission, we will examine the difference in adjusted predicted probability of having a new BZR prescriptions from admission to discharge

between the intervention group and the control group. We will use logistic regression using a generalized estimating equations approach and estimate adjusted predicted probabilities.³ We hypothesize that among patients without a BZR prior to hospitalization, the risk-adjusted probability of having a new discharge BZR prescription will be substantially lower (e.g. 35% lower) among patients who are enrolled in the PHARM-DC intervention compared to the control group.

2. Among patients taking BZRs prior to hospitalization, we will use logistic regression to estimate the adjusted predicted probability of dose intensification among patients in the PHARM-DC intervention and the control group.³ We hypothesize that among patients with BZRs prior to hospitalization, the risk-adjusted probability of experiencing a dose increase will be substantially lower (e.g. 35% lower) among patients who are enrolled in the PHARM-DC intervention compared to controls.

Outcome measures: We will create two measures: (1) a dichotomous variable for a new discharge prescription of BZRs among patients not taking BZRs prior to admission, and (2) a dichotomous variable for an increased dose prescription among patients taking BZRs prior to admission.

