2. Minimal Risk: The risks to the patients are minimal. After the medication history is taken for patients, the patients are randomized into either the treatment or control group. However, if a clinician believes that the patient would benefit from the pharmacist consult and/or post-discharge phone call, the patient will meet with the pharmacist regardless of whether they are in the study. Thus, any patient who needs the pharmacist services will receive the appropriate care. The pharmacist participating in the intervention will provide a consult to the physician about medications that should be changed, but the physician will have the final say about any medication changes. This is equivalent to the physician consulting an online resource or receiving a computerized alert about medication recommendations (clinical decision support). Participating in the study will not adversely affect the rights or welfare of the participants since patients who request a meeting with a clinical pharmacist or situations where the attending physician believes the patient should meet with the clinical pharmacist will have every right to do so.
3. Reducing Risk: Since this study is a very low risk intervention, we believe that adding a signed consent form would actually introduce more risk because it would now introduce a document that could identify the participants. We are planning on analyzing the study data at the completion of the intervention and the data will be extracted and only accessed by select study staff. Incorporating documents with PHI may increase the risk for patients of loss of confidentiality.
4. Decrease of Data Validity and Quality: Patients who are randomized to the control group may be more likely not to participate in the study (a phenomenon known as “resentful demoralization”) so there may be systematic bias introduced if patients are asked to consent, which could decrease the validity of study results [see Rebers S, Aaronson NK, Van Leeuwen FE, Schmidt MK. Exceptions to the rule of informed consent for research with an intervention. *BMC medical ethics*. 2016 Dec;17(1):9.].

The risk to subjects is no more than minimal risk to privacy. We have put several measures in place to protect the privacy of subjects and confidentiality of the data:

[1] Personally identifying information will only be available to study personnel.

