[2] All identifiable (and de-identified) data will be in electronic format. These data will be stored and used entirely within CSMC computer systems on the CSMC network, where appropriate technical safeguards (including authentication, security and virus protection) are in place. Since the data originates on this network, the increase in risk is minimal.

[3] All identifiers will be destroyed at the end of the study (the research data itself will be kept for seven years after completion of the research).

During training, trainers will emphasize to pharmacists participating in this study additional, clinically-indicated services may be provided to control group patients to ensure that it is clear that routine services that are part of the PHARM-DC and that the toolkit should not be withheld from the control group if they are clinically indicated. This will ensure that patients in the control group will receive appropriate services if needed.

Focus Groups and Interviews

For the focus groups, we will provide an information sheet outlining the purpose, risks, and benefits of the study intervention. A member of the study staff will go over the information sheet.

Information sheets will be Institutional Review Board (IRB)-approved, and the participant will be asked to read and review the document. The investigator will explain the research study to the participant and answer any questions that may arise. A verbal explanation will be provided in terms suited to the participant's comprehension of the purposes, procedures, and potential risks of the study and of their rights as research participants. Participants will have the opportunity to carefully review the written information sheet and ask questions prior to participating in the focus group. Participants will be informed that participation is voluntary and that they may withdraw from the study at any time, without prejudice.

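### Section 8.4.4 costs controls at zero although they may receive the same pharmacist services, so incremental program cost is overstated: about 2% at the plan's own contamination figure, more only if such services are commoner

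*Combined protocol and SAP*

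**What the plan says.** Aim 3 (sections 1.1 and 1.2) asks for the incremental cost per readmission averted and the net incremental cost to the health system. Section 8.4.4 produces two results:

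- **Cost per event averted:** the NNT multiplied by the cost of giving the intervention to one patient.
- **Net cost:** a per-patient figure built from program cost and utilization cost, then compared between arms. Here "program costs are zero in the control group".

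Other sections describe what controls may receive:

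- Section 1.3, control arm: "Will receive usual care, which may include pharmacist consultation and/or after-discharge phone call(s) if clinically necessary".
- Section 9.1.1, on training (also in the synopsis): routine program services and "the toolkit should not be withheld from the control group if they are clinically indicated".
- Section 9.1.1, on minimal risk: if a clinician sees a benefit, "the patient will meet with the pharmacist regardless of whether they are in the study".
- Section 1.3: both arms receive the Best Possible Medication History (BPMH).

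Section 8.4.4 also plans "40 observations of usual care" at each site, and section 1.3 has observers contrast program time with time spent on usual-care patients. Neither cost formula states a use for the usual-care time.

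**The concern.** An incremental cost is the cost in one arm minus the cost in the other, measured by the same rule. Here the intervention arm is charged for pharmacist labor and the control arm is not, although the protocol expects some controls to use that labor. The NNT comes from the randomized contrast, in which any benefit of control-arm services has already narrowed the difference. Multiplying that net effect by a gross cost gives a ratio whose two parts refer to different comparisons.

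Control-arm labor cannot cost less than nothing, so leaving it out can only make the program look dearer than it is. Section 2.1 presents the trial as a way to strengthen a weak business case, so hospital leaders will read this figure closely.

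**Working it through.** **Design figures behind the NNT.** Section 8.2 gives 27.5% versus 25.01%, two-sided alpha 0.05, 80% power and 4,888 per group. With pooled variance and no continuity correction:

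n = [1.960·√(2·0.26255·0.73745) + 0.8416·√(0.275·0.725 + 0.2501·0.7499)]² / 0.0249² = 4,901 per group.

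This is 0.3% from the stated figure, and power at 4,888 is 79.9%, so the plan's number reproduces. At the design effect, NNT = 1/0.0249 = 40.2. The documents state no program cost, so costs below are in units of P.

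**Inputs.**
- P: program cost per intervention patient (not given).
- c: share of controls given comparable services. The only figure is in section 8.2: "these rates were robust to contamination rates of 2% among patients in the usual care arm". It is a share of patients, not of cost.
- r: cost of those services relative to P (not given; 0.5 and 1 are shown as assumptions).

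**Formulas.**
- Plan: incremental program cost = P − 0 = P; cost per event averted = NNT·P.
- With control labor counted: P − c·r·P = P(1 − c·r); cost per event averted = NNT·P(1 − c·r).
- Relative overstatement of both: 1/(1 − c·r) − 1. The NNT cancels.
- Error in incremental net cost: c·r·P per patient. The percentage formula does not apply there, because net cost also contains the difference in utilization cost.

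**Results.** The plan's cost per event averted is 40.2P in every row.

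| c | Source of c | Overstatement, r = 0.5 | Overstatement, r = 1 | Corrected cost per event averted, r = 1 |
|---|---|---|---|---|
| 2% | section 8.2 | 1.0% | 2.0% | 39.4P |
| 5% | assumed | 2.6% | 5.3% | 38.2P |
| 10% | assumed | 5.3% | 11.1% | 36.1P |
| 20% | assumed | 11.1% | 25.0% | 32.1P |
| 30% | assumed | 17.6% | 42.9% | 28.1P |

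At c = 2% and r = 1 the error in incremental net cost is 0.02P per patient.

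**BPMH.** Section 8.4.7 calls admission medication reconciliation a key component of the intervention, and section 1.3 gives it to both arms. Section 8.4.4 does not say whether its time counts within a complete intervention. If it does, every control incurs that part of the cost too.

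**A separate sign problem in the same sentence.** Net cost is described as program cost with utilization cost subtracted. To illustrate, assume P = 100 and 10,000 per event. Taken literally, the between-arm difference is (100 − 2,501) − (0 − 2,750) = +349. Adding the two costs gives (100 + 2,501) − (0 + 2,750) = −149. Read literally, averted events raise the incremental cost. On these assumed values the gap is far larger than the control-cost error, which is 2 per patient at c = 2% and r = 1.

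**The case against.** **The effect may be negligible.** Section 5.2 excludes patients "Expected to receive pharmacist-led post-discharge medication management regardless of the trial", and section 8.2 treats 2% contamination as reasonable. This limits the size, and at 2% the error is small. It does not make the cost zero. The exclusion concerns expected post-discharge management, not in-hospital consultations or needs that arise after randomization. Section 8.2 argues partly from non-pharmacist clinicians being too busy, which does not cap the pharmacist contacts allowed by sections 1.3 and 9.1.1.

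**Zero may be a matter of definition.** Program cost could mean only the labor of pharmacists implementing PHARM-DC, which controls lack by label. This reading is possible, but the result is then a gross cost and does not answer the incremental question in Aim 3.

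**Silence is not exclusion.** A reader might infer that the usual-care observations are discarded. The text does not say so. It only fails to specify a use for them.

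**The overall direction is unknown.** A reader might infer that the Aim 3 results as a whole are biased against the intervention. The documents do not support that. Section 8.4.4 totals time by post-discharge day, which may omit in-hospital time and understate P. Costing everyone at complete-intervention time, when section 8.2 considers 7.5% unreachable or refusing a call, would overstate P. The sign problem affects net cost separately.

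**Conclusion.** The inconsistency is real. The stated rules charge pharmacist labor to one arm only, although the protocol lets the other arm use it, and the result is called incremental. Taken alone, this overstates incremental program cost and cost per event averted by about 2% at the plan's 2% contamination if control services cost as much as the intervention, and by about 1% if they cost half as much. In incremental net cost it adds c·r·P per patient.

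It is tempting to quote an overstatement of 11% to 43%. Those figures need 10% to 30% of controls to receive services as costly as the full intervention, and no document gives such a rate. They show only what would follow if control services proved common.

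The point merits correction because the rule does not match the stated aim and most of the needed data are already planned, not because a large error has been shown.

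**What to change.** In section 8.4.4:

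1. Delete the parenthesis stating that "program costs are zero in the control group". Assign each patient in both arms the cost of the pharmacist discharge and post-discharge services documented for that patient. Use observed mean times, taken from the usual-care observations for controls, and run the Epic note and call reports of section 6.3 for both arms.
2. State whether BPMH is left out of both arms or counted in both.
3. Compute net cost per patient from these arm-specific costs and difference the arms once. Program cost must not also be defined as a between-arm difference at this step, or control cost would be subtracted twice.
4. For cost per event averted, multiply the NNT by the intervention-minus-control difference in mean pharmacist cost.
5. In the same edit, correct the wording that subtracts utilization cost from program cost.

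The cost is a few sentences and one further run of the Epic report. The control-arm estimate adds some uncertainty. It also depends on the planned observations covering the relevant services, and on control contacts being documented in Epic comparably with intervention contacts, which section 6.3 does not establish. If they are not, report a sensitivity range over c and r. If control use proves close to zero, the analysis will have shown it instead of assuming it.

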8.4.7 SECONDARY DATA ANALYSIS: PROPENSITY SCORE ANALYSIS AT BRIGHAM AND WOMEN'S HOSPITAL

Admission medication reconciliation is theorized to be one of the key components of the PHARM-DC intervention that may contribute to reduced 30-day post-discharge utilization. At the Brigham and Women's Hospital (BWH) site, many more patients were eligible for enrollment in the PHARM-DC clinical trial than were actually enrolled due to limited pharmacist staff bandwidth. For this reason, patients who were eligible, yet were not enrolled, did not receive admission medication reconciliation (also known as a "Best Possible Medication History" [BPMH] in the literature).

As a secondary analysis of trial data, we propose to compare patients who were eligible for trial enrollment *and* enrolled to patients who were eligible *and not* enrolled at BWH. We will perform a propensity score analysis to predict enrollment into the PHARM-DC clinical trial at the individual patient-level. Resulting propensity scores will then be used to identify matches between patients at BWH who were eligible and enrolled vs. eligible and not enrolled during the study period for comparison. The outcome of interest is 30-day post-discharge utilization (same hospital).

Data will be retrieved retrospectively from the electronic health record at BWH as previously described in this IRB protocol. Specifically, variables in the propensity model will include:

1. Time of day of hospital admission
2. Day of week of hospital admission
3. Day of week of hospital discharge
4. Admit type
5. Admit service
6. Discharge service
7. Hospital length of stay
8. Discharge location
9. Admissions medications list
10. High-risk medications list at admission
11. Calendar quarter
12. Insurance type
13. Admission source
14. Interaction effect between length of stay *and* day of week of admission

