1.3 SCHEDULE OF ACTIVITIES (SOA)

(1) *Pharmacist-led Hospital Discharge Care Intervention:*

- a. Eligible pharmacists at each study site will be selected to participate in the intervention based on their training in transitions of care.
- b. Using a daily Epic report generated by EIS, a coordinator at each site will identify eligible patients and notify pharmacists. Trial enrollment will occur for eligible patients admitted every day prior from Monday to Friday.
- c. Randomization will be performed via the REDCap (Research Electronic Data Capture) system.
- d. All eligible patients (both arms) will receive the Best Possible Medication History (BPMH)
- e. Patients in the Study arm:
 - i. On hospital day 1, or as soon as possible: Receive an Initial Medication Regimen Assessment. Clinical pharmacists assess regimen appropriateness, assess barriers to medication adherence, start filling out the Actions for Assessing Adherence Barriers worksheet
 - ii. On hospital day 1, or as soon as possible: Receive a Pre-Discharge Intervention, which, depending on the patient condition, might include a: trial to discontinue certain medications during the hospital; discussion of side effects, flags for new medications prescribed, education about critical barriers to adherence.
 - iii. On day of discharge: Receive an At-Discharge Intervention, which may include a brief discussion of medication changes, discussion of side effects, discussion of red flags for new medications. Clinical pharmacists will also consult with inpatient clinicians and pharmacists to discuss the medication list and will ensure that the e-prescribing is done appropriately.
 - iv. 1-3 days after discharge: Receive a Post-Discharge Intervention, which includes a call with a patient to discuss the patient's regimen, discussion of side effects, red flags of new medications, a motivational interview, a discussion of barriers to adherence. Other tasks might include a phone call with the patient's primary care physician.
 - v. After initial phone call: Some patients, depending on need, might receive a second phone call if needed, a video visit, clinic visit with pharmacist, embedded mental health.
 - vi. For any of the above-mentioned activities, patients may be contacted by pharmacists over the phone instead of in-person to reduce COVID-19 exposure to patients, caregivers, and pharmacists.
- f. Patients in the Control arm:

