6.2 MEASURES TO MINIMIZE BIAS: RANDOMIZATION AND BLINDING

Randomization will be performed via the REDCap (Research Electronic Data Capture) system. REDCap is a secure, web-based application supporting data capture for research studies, providing:

- 1) an intuitive interface for validated data entry;
- 2) audit trails for tracking data manipulation and export procedures;
- 3) automated export procedures for seamless data downloads to common statistical packages; and;
- 4) procedures for importing data from external sources.

REDCap will incorporate allocation tables generated in R. Study participants will be randomized 1:1 to the two arms of the study and stratified by site. Arm assignment will not be actively masked, but most clinical personnel and patients will remain unaware of the trial, just as they are unaware of the details of most post-discharge medication management practices currently.

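### The BWH propensity analysis (8.4.7) is motivated by admission medication reconciliation but pools both trial arms, so it estimates an effect of enrolment and not of reconciliation; its covariate list also omits age, sex, comorbidity and prior admissions

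*Combined protocol and SAP*

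**What the plan says.** Section 8.4.7 opens with its rationale: "Admission medication reconciliation is theorized to be one of the key components of the PHARM-DC intervention". The one difference in care that it names between the groups is that "patients who were eligible, yet were not enrolled, did not receive admission medication reconciliation". The analysis models the propensity to be enrolled, then uses the scores to "identify matches between patients at BWH who were eligible and enrolled vs. eligible and not enrolled during the study period". The outcome is same-hospital utilization within 30 days. No restriction or stratification by randomized arm is stated, there or elsewhere.

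Three other sections fix what the enrolled group consists of. Section 1.3 says: "All eligible patients (both arms) will receive the Best Possible Medication History (BPMH". Section 9.1.1 gives the order: "After the medication history is taken for patients, the patients are randomized into either the treatment or control group". Section 6.2 gives the ratio: "Study participants will be randomized 1:1 to the two arms of the study and stratified by site".

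The propensity model has 14 numbered items: timing and type of admission, discharge day, services, length of stay, discharge location, medication lists, calendar quarter, insurance, admission source and one interaction. On data, the section says only "Data will be retrieved retrospectively from the electronic health record at BWH as previously described in this IRB protocol".

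**The concern.** The rationale points to one exposure, BPMH, while the groups differ in two. Every enrolled patient was due BPMH, and about half were also assigned the PHARM-DC assessment, counselling and post-discharge call. Matching on the propensity to enrol cannot separate the two, because arm is allocated at random among the enrolled. A favourable result would naturally be read as support for admission reconciliation, since that is the reason given for doing the analysis, although part of it could come from PHARM-DC.

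Separately, the comparison is not randomized, and the listed covariates leave out four ordinary predictors of 30-day utilization. Section 8.4.7 also states no balance check after matching.

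**Working it through.** **Inputs.** Planned effect 2.5 points from a 27.5% baseline (Sections 3 and 8.1). Allocation 1:1, stratified by site (6.2). BPMH in both arms (1.3, 9.1.1). Usual-care contamination 2%, and 7.5% of the intervention arm not reached or refusing the call (8.2). BWH enrolment and the matching ratio are not given.

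**The plan's own figure.** Section 8.4.7 has no sample size, so the check is on the trial calculation that supplies the effect size. For 27.5% versus 25.01%, two-sided 0.05, 80% power, pooled variance:

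n = [1.960 × √(2 × 0.26255 × 0.73745) + 0.842 × √(0.275 × 0.725 + 0.2501 × 0.7499)]² / 0.0249² ≈ 4,901 per group

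The stated 4,888 gives 79.9% power, so the figure reproduces.

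**What the pooled contrast contains.** Let I, C and N be the mean outcomes in the BWH intervention arm, the BWH usual-care arm and the matched non-enrolled patients. With share s of the enrolled in the intervention arm:

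enrolled − N = s·I + (1 − s)·C − N = (C − N) + s·(I − C)

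C − N is the BPMH contrast, provided other pharmacist services are similar in those two groups and confounding is controlled. I − C is the effect that the trial itself estimates. Under 1:1 allocation s ≈ 0.5. The identity needs only that both arms receive BPMH.

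**Size of the PHARM-DC part.**
- Planned effect: 0.5 × 2.5 = 1.25 points.
- Assumed s from 0.45 to 0.55: 1.13 to 1.38 points.
- Effect scaled to 92.5% delivery: 0.5 × 0.925 × 2.5 = 1.16 points.
- Taking 2.5 points as the effect of receipt, with 2% contamination in usual care and none among the non-enrolled: 1.25 + 0.5 × 0.02 × 2.5 = 1.275 points. One half is therefore an approximation and not a strict maximum.
- Holding I − C at 2.5, each assumed 10-percentage-point gap in other services between usual-care and non-enrolled patients moves C − N, and with it the pooled contrast, by 0.10 × 2.5 = 0.25 points in either direction. The documents state no such gap.

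**Share of the result.** With an assumed true BPMH effect of 0, 0.5, 1.0 or 2.5 points, the pooled contrast is 1.25, 1.75, 2.25 or 3.75 points, of which 100%, 71%, 56% or 33% comes from PHARM-DC.

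**Scale.** The 2.5 points refer to same-state readmissions and ED visits. Same-hospital utilization, as Section 3 defines it, also counts observation stays. The documents give no conversion.

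**Covariates, side by side.** None of the 14 items is age, sex, a comorbidity measure or prior admissions. Appendix A has all four: date of birth (item 9), sex/gender (29), a Charlson or Elixhauser index (5) and the count of admissions over the preceding 3 years (6).

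**Precision of a one-arm contrast.** With n exposed patients and k matches each, the variance is proportional to (1/n)(1 + 1/k). Halving n at the same k multiplies the standard error by √2 = 1.41.

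**The case against.** Section 8.4.7 writes out no BPMH estimand or hypothesis. It defines one contrast, enrolled versus not enrolled, models enrolment, and describes BPMH as one component among several. Read that way, the mixture is the target and only a label is missing. This stands in part: the fault is a mismatch between rationale and contrast, not an error in a declared estimand. It does not remove the problem, because the section names BPMH and no other difference between the groups.

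On the covariates, the documents attribute non-enrolment mainly to pharmacist capacity (8.4.7; Section 5.3 stops randomization when workload is exceeded). The timing variables model that mechanism. No section says that enrolment among eligible patients depended on age, sex or comorbidity. The medication lists carry some comorbidity information, and the list need not be exhaustive. These points stand as far as they go, but medication lists do not capture sex or prior admissions, and a numbered list that extends to an interaction term reads as the intended model.

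A reader might infer that the omission biases the result. The documents do not show that, and such a bias cannot be sized from them. A reader might also suppose that non-enrolled patients received more pharmacist services than controls, which would shrink the carry-over. The documents give no basis for that asymmetry: Sections 1.1, 1.3 and 9.1.1 allow clinically indicated services in the control arm, and where a clinician sees a benefit, "the patient will meet with the pharmacist regardless of whether they are in the study".

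**Conclusion.** The point holds as a minor one about a secondary analysis. The pooled contrast is the BPMH effect plus about half of the PHARM-DC versus usual-care effect, or about 1.25 points at the planned effect. This assumes 1:1 allocation carried into the matched set, similar other services in usual-care and non-enrolled patients, and the same-state scale. The contrast is an effect of enrolment and should not be reported as an effect of BPMH. The four missing covariates are a risk of confounding only.

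Two stronger readings are not supported. How often a null BPMH effect would come out nominally significant cannot be stated, because neither BWH enrolment nor the matching ratio is given. Nor is there any consequence for the trial's main result: the primary randomized comparison is unaffected.

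**What to change.** 1. Report the BWH usual-care arm versus matched non-enrolled patients as the BPMH contrast, and the intervention arm versus matched non-enrolled patients as BPMH plus PHARM-DC. If the pooled contrast is kept, label it an effect of enrolment.
2. Add age, sex, a comorbidity index and prior admissions to the propensity model, and report covariate balance after matching. Confirm that these fields can be extracted for non-enrolled patients; the documents do not say that the Appendix A extract covers them.
3. Optionally, add a sensitivity analysis without the variables fixed after admission (items 3, 6, 7, 8 and 14). They should not simply be dropped: length of stay bears on the chance of enrolment, and expected discharge destination is part of eligibility in Section 5.2.

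The cost is SAP wording and one check of data availability. The downside is precision: using one arm halves the exposed sample, so the standard error of the BPMH contrast is about 41% higher at the same matching ratio.
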